4.5.2 Ambulatory Performance

The 10 meter walk test will be conducted at Day 90 visit to measure patient's walking speed. The speed will be measured at a comfortable pace and a fast pace, giving two attempts for each pace level. Average speed from the two attempts obtained at each pace will be summarized descriptively by treatment group. If speed can only be calculated in one of the attempts at a pace level, this result will be used.

Average speeds will be summarized by treatment group (mean, standard deviation, median, quartiles, minimum and maximum). Mean difference between treatment groups with 95% unadjusted normal CI will be presented. Reasons for the assessment not being performed will be summarized by the number and percentage in each category.

4.5.3 Patient Reported Outcomes

The patient reported outcomes (PROs) for this study include the EQ-5D, the 16 item Stroke Impact Scale (SIS-16), and the Center for Epidemiologic Studies Depression Scale (CES-D).

4.5.3.1 EQ-5D

Health-related quality of life will be assessed using the EQ-5D. The EQ-5D is a generic, preference-based health utility measure with questions about mobility, self-care, usual activities, pain/discomfort, and anxiety/depression that are used to build a composite of the patient's health status. The second component of the EQ-5D is a visual analogue scale (VAS), asking patients to rate their health from 0 to 100 where 0 represents the worst imaginable health state and 100 represents the best imaginable health state.

Each question is scored as 1 for no problem, 2 as some problem, and 3 indicating extreme problem. Ambiguous values (eg. 2 boxes are ticked for a single dimension) will be treated as missing (neither value used).

The 5 scores will then be converted into a single summary index by applying the time trade-off valuation technique for the US, published by EuroQol group. SAS

Statistical Analysis Plan: Alteplase—Genentech USMA
23/ML29093 5/17/2017

code to perform the calculation is provided in [Appendix G](#). The resulting summary index is a continuous variable ranging from -0.11 (i.e., 3 for all questions) to 1.0 (i.e., 1 for all questions) on a scale where 0.0 = death and 1.0 = perfect health (18). If any of the 5 scores are missing, the summary index will not be calculated and set to missing.

The VAS is scored by the crossing point of the VAS with the response line, or with a horizontal line extended from the end point of the response line. Ambiguous values (eg. the line crosses the VAS twice) will be treated as missing.

Scores to each question, the summary index, and the VAS result, will be summarized descriptively, and the two-sided 95% CI of the mean difference will be presented for the index and VAS.

4.5.3.2 Stroke Impact Scale-16 (SIS-16)

Physical functioning will be evaluated using the SIS-16, which is a validated, stroke-specific, quality of life measure to assess the impact of stroke on a patient's health and life. Each of the 16 items is rated using the following scale: 1 = could not do at all; 2 = very difficult; 3 = somewhat difficult; 4 = a little difficult; 5 = not difficult at all.

The physical domain score is obtained by averaging the non-missing responses, provided that 9 or more questions are answered. The score is calculated as:

$$\text{Score} = 100 \times [(\text{Mean} - 1) / (5 - 1)]$$

which ranges from 0 to 100 (19).

Responses to individual questions and the physical domain score will be listed. The domain score will be summarized by treatment group and the two-sided 95% CI of the mean difference will be presented.

4.5.3.3 Center for Epidemiologic Studies Depression Scale (CES-D)

The CES-D is a short, self-report scale designed to measure depressive symptomatology. Responses to the 20 individual items will be scored to obtain an overall depression assessment, as follows.

1. Assign scores 0 = rarely or none of the time, 1 = some or little of the time, 2 = occasionally or moderate amount of time, 3 = most or all of the time.

Statistical Analysis Plan: Alteplase—Genentech USMA
24/ML29093 5/17/2017

2. Reverse positive items by subtracting their score from 3. Positive items are 4, 8, 12, and 16.
3. If 4 or fewer items are missing, sum the available item scores to determine the total score. If more than 4 items are missing, no score is calculated.

The total score will be used to evaluate the proportion of patients with depressive symptoms (defined as a score of ≥ 16 at 90 days) and will be summarized by treatment group.

Observed percentages and adjusted odds ratio will be presented. The adjustment will be performed in the same way as for the exploratory analysis of mRS 0-1.

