2.2.3 Exploratory Efficacy Outcome Measures

The following exploratory outcome measures for this study are measured at day 90 and included in the analyses described in this SAP:

- Total score of NIHSS at day 90
- Instrumental activities of daily living, as measured by the Total score of the BI at day 90
- Raw score of the GOS at day 90
- Cognition and behavior (modified 30-minute battery):
 - Controlled Oral Word Association test;
 - Hopkins Verbal Learning Test-Revised [HVLTR] trials 1, 2, and 3;
 - digit symbol coding from the Wechsler Adult Intelligence Scale III [WAIS III]; Forward and Backward Digit Span test;
 - Benton Judgment of Line Orientation test, form V;
 - HVLTR trial 4 and recognition;
 - semantic fluency [Animal Naming test];
 - Boston Naming Test [BNT; 15-item short form]
- Ambulatory performance (as measured by walking speed)
- Depression (CES-D [Center for Epidemiologic Studies, Depression]) score
- Quality of Life (EQ-5D [European Quality of Life] questionnaire)
- Stroke Impact Scale-16 (SIS-16)

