4.4 EFFICACY ANALYSES

All efficacy analyses will be to estimate treatment effects and provide the associated two-sided 95% confidence intervals.

Statistical Analysis Plan: Alteplase—Genentech USMA
13/ML29093 5/17/2017

Endpoints based on mRS will generally use imputation to achieve the complete ITT set, with the exception of the repeated measures modeling. Other efficacy variables will use all available data in the ITT population.

Assessment of efficacy will be conducted based on endpoints collected during the Day 90 visit. The protocol allows this visit to be scheduled within 14 days of the target 90 days post-treatment; however, a wider window of 30 days will be adopted for the purpose of efficacy analysis.

More details of imputation approach for mRS are provided in Section 4.7 and Appendix D.

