4.4.3.5 Barthel Index

The BI total score will be used to evaluate the proportion of patients with complete independence (defined as a score = 100) and will be summarized by treatment group. Observed percentages and adjusted risk difference will be presented. The adjustment will be performed in the same way as for the primary endpoint. Reasons for not performing the assessment of BI will be summarized.

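### The CES-D is listed as a score outcome, but its treatment effect is estimated only at the cut-off of 16; a mean difference with 95% CI, as given to the other patient-reported scores, is missing.

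*SAP*

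**What the plan says.** Section 2.2.3 of the SAP lists among the exploratory efficacy outcomes "Depression (CES-D [Center for Epidemiologic Studies, Depression]) score".

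Section 4.5.3.3 scores the 20 items 0 to 3, reverses the positive items and sums them, allowing up to four missing items. The total is then used through one threshold: "The total score will be used to evaluate the proportion of patients with depressive symptoms", with "depressive symptoms (defined as a score of ≥ 16 at 90 days) and will be summarized by treatment group". The effect measure follows: "Observed percentages and adjusted odds ratio will be presented". The adjustment is that of the exploratory logistic analysis of mRS 0-1. No between-arm difference in the total score is planned.

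The neighbouring sections work differently. Sections 4.5.1 (cognitive tests) and 4.5.2 (walking speed) plan a mean difference with an unadjusted 95% CI. Sections 4.5.3.1 (EQ-5D index and VAS) and 4.5.3.2 (SIS-16) plan a 95% CI for the mean difference.

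The Barthel Index and the NIHSS are also named as total scores in 2.2.3, the former with the words "as measured by the Total score of the BI at day 90". Section 4.4.3.5 says: "The BI total score will be used to evaluate the proportion of patients with complete independence", that is, a score of 100. Section 4.4.2.2 adds BI of 95 or more as a component of the global outcome, with its own adjusted odds ratio. Section 4.4.3.4 summarises the NIHSS score by arm and estimates effects at 0 and at 0-1.

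**The concern.** The outcome list names a score, but the analysis section estimates an effect on something narrower. Within section 4.5 the CES-D is the only patient-reported measure handled this way.

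This matters more here than in a fully recruited trial. Section 2.3 says the study is substantially underpowered after stopping at 313 patients and rests the efficacy analysis on estimates and confidence intervals, so interval width is the main thing the analysis can deliver. The total runs from 0 to 60 (20 items, maximum 3 each). A single threshold counts a patient at 15 and one at 16 as different, and treats patients at 20 and at 40 as alike. A treatment effect that moves scores on one side of the threshold leaves the odds ratio unchanged.

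**Working it through.** **What the SAP gives.** It states no CES-D rate, mean, SD or power, so there is no figure of its own to reproduce on this point. The only usable number is the count of patients with a Day 90 outcome in Table 1: 313 × (1 − 0.074) = 289.8, or 290 as stated. That is the mRS figure, and I assume it applies to the CES-D.

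**Formula.** Let p be the proportion scoring 16 or more. For a roughly normal score and a small shift between arms, the efficiency of the cut-off relative to the mean difference is

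ARE = φ(z_p)² / [p(1 − p)],

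where φ is the standard normal density and z_p the normal quantile at p. Information lost is 1 − ARE. Equivalent sample size is 290 × ARE. The interval on a common scale widens by 1/√ARE.

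For p = 0.20: φ = 0.280, so ARE = 0.0784/0.16 = 0.49.

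| p (assumed) | ARE | Lost | Worth, of 290 | Interval width × |
|---|---|---|---|---|
| 0.10 | 0.342 | 66% | 99 | 1.71 |
| 0.15 | 0.426 | 57% | 124 | 1.53 |
| 0.20 | 0.490 | 51% | 142 | 1.43 |
| 0.25 | 0.539 | 46% | 156 | 1.36 |
| 0.30 | 0.576 | 42% | 167 | 1.32 |
| 0.35 | 0.603 | 40% | 175 | 1.29 |
| 0.40 | 0.622 | 38% | 180 | 1.27 |
| 0.50 | 0.637 | 36% | 185 | 1.25 |

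**In SD units.** With 145 per arm, the 95% half-width of a mean difference is 1.96 × √(2/145) = 0.23 SD. At p = 0.25 the cut-off gives 0.23 × 1.36 = 0.31 SD.

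**Skewed scores.** The normal shape is doubtful for a symptom scale, so the calculation was repeated with right-skewed gamma scores (assumed means 8 to 14, SDs 8 to 11, giving p from 14% to 35%). If treatment scales all scores proportionally, ARE is 0.624 to 0.645, a loss of about 36% to 38%. If it shifts all scores by a constant, ARE is 0.168 to 0.509, a loss of 49% to 83%. At least about one third was lost in every case tried.

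**The case against.** The best defence is that 2.2.3 lists what is measured and does not fix the effect measure. Section 4.5.3.3 starts from the same total score and pre-specifies the threshold, so this is an analysis choice and not an outright contradiction. That stands. What remains is that the choice differs, without explanation, from every other score in section 4.5.

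Second, the proportion above a threshold and the mean are different estimands, and the efficiency comparison is like for like only if treatment shifts the whole distribution. Also correct; it is why the threshold should stay and the mean difference be added.

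Third, a reader might infer that the CES-D score will go unreported. The SAP does not support that. Section 4 promises descriptive statistics for all endpoints, and 4.5.3.3 can be read as summarising the total by arm. With n, mean and SD by arm, an unadjusted interval could be worked out by hand. What is missing is the planned estimate.

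Fourth, a reader might cite the opening of section 4.4: "All efficacy analyses will be to estimate treatment effects and provide the associated two-sided 95% confidence intervals". That sentence heads 4.4, while the CES-D analysis sits in 4.5. The odds ratio is in any case an effect estimate.

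Fifth, a reader might extend the point to the Barthel Index and NIHSS with the same force. Each has between-arm estimates at two cut-offs, scores in mild stroke are likely to pile up near the best value, and the normal formula should not be carried over to them. For these two, an estimate on the total score is closer to preference.

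**Conclusion.** The point holds for the CES-D. Its treatment effect is estimated only at one cut-off, while every other patient-reported score, the cognitive tests and walking speed get a mean difference with a 95% CI.

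The loss of information on a shift in the score is about 36% to 66% if the score is roughly normal and 10% to 50% of patients score 16 or more. It would be tempting to quote 40% to 50% as the loss, but that band needs a rate of about 20% to 35% as well as near-normality, and the SAP supplies neither. No loss is quantified for the Barthel Index or NIHSS.

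The outcome is exploratory and no main conclusion of the plan depends on it, so this is a minor improvement.

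**What to change.** In section 4.5.3.3, add the between-arm mean difference in CES-D total score with a two-sided 95% CI. It can be unadjusted, matching the cognitive tests and walking speed, or adjusted with the ordinary least squares, robust standard error model of section 4.4.1. The SAP should say which. Keep the cut-off of 16 with its percentages and odds ratio as the responder analysis.

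For the Barthel Index and NIHSS, a between-arm estimate on the total score is optional. If none is added, reword 2.2.3 so that it names the cut-offs actually analysed: BI at 100 and at 95 or more, NIHSS at 0 and at 0-1.

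The cost is a few lines of SAP text and one table row from data already collected, using a method already in the SAP. The downside is one more exploratory estimate.

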4.6 SAFETY ANALYSES

MedDRA (using the latest version at the time of reporting) will be used as the thesaurus for AEs and diseases, and the World Health Organization (WHO) drug dictionary will be used for treatments and MedDRA for procedures. A glossary of these codes will be produced.

AEs with onset prior to initiation of study treatment which do not worsen after study treatment or with onset after Day 90 assessment, will be listed as non-treatment emergent and will not be included in the safety summaries.

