2.2.4 Safety Outcome Measures

The safety outcome measures for this study are as follows:

- Symptomatic Intracranial Hemorrhage (sICH) within 36 hours of receiving IV study drug (primary safety assessment)

sICH is defined as any neurological decline attributed to new ICH seen on imaging by the investigator (based on AE reporting). New ICH seen on imaging will be later confirmed on independent reading by blinded central study radiologists
- Any ICH (based on central neuroimaging reading) within 36 hours of receiving IV study drug
- Mortality within 90 days

Statistical Analysis Plan: Alteplase—Genentech USMA
7/ML29093 5/17/2017

- Stroke-related and neurological deaths within 90 days
- Incidence, severity, and spectrum of all adverse events (AEs) and serious AEs (SAEs).

The exploratory safety measure for this study is:

- Stroke recurrence (based on AE monitoring) within 90 days

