4.6.2 Adverse Events

AE safety endpoints in this study are:

- Number and percentage of patients experiencing serious and non-serious AEs after receiving study drug
- Number and percentage of patients experiencing serious and non-serious AEs of special interest

AEs will be coded (using the latest MedDRA version at the time of reporting) and tabulated by system organ class (SOC); individual events within each SOC coded as preferred terms will be presented in descending frequency using the safety population. Treatment groups will be summarized according to the actual treatment received.

AEs will also be tabulated by intensity (severity) and relationship to study drug, as indicated by the investigator. Intensity of AEs will be graded according to the WHO Toxicity Grading Scale for Determining the Severity of Adverse Events (see Appendix 14 of the protocol). Incidence and severity of AEs will be described for all treated patients by treatment group and by the MedDRA classification.

A summary of incidence rates of all deaths and stroke-related or neurological deaths will be presented. Cumulative incidence of all deaths and stroke-related or neurological deaths will be presented by means of Kaplan-Meier plots if there are sufficient events (at least 5 in each group).

Timing of the AEs relative to Day 30 and Day 90 will be determined, using imputation for partial AE start and stop dates if necessary, as described in [Appendix D](#). AEs occurring after receipt of any study medication and before Day 90 will be summarized. AEs leading to IV study drug modification will be listed. SAEs, ICH, AEs of special interest and AEs leading to study treatment discontinuation will be summarized through Day 90. In addition, non-serious AEs within 30 days will be summarized.

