Appendix D

Statistical Methods Requiring Input

Handling of incomplete start and stop dates of adverse events

A missing day in a start date will be imputed with the first day of the month, but not earlier than the randomization date. A missing day in a stop date will be imputed with the last day of the month.

A missing month/year in a start date will be imputed by the month/year of randomization. A missing month in a stop date will be imputed by the month of the last contact. A completely missing stop date will be treated as an ongoing AE and will not be imputed.

Determination of ICH and sICH events

For ICH and sICH events, the following rules will be used to determine their timing relative to 36 hours:

- For ICH determination by scan reading (local or central), take the earliest post-baseline scan with bleeding identified. Use the evaluation time of that scan to compare to 36 hours.
- For ICH determination by AE reporting, take the start date of the corresponding AE. Then find all scans with the same date of local reading, where bleeding is identified. Take the earliest such scan and use the evaluation time of that scan to compare to 36 hours. If no scan is found, use 12:00 am on the AE start date to compare to 36 hours.

When there are multiple scans associated with a PH2 bleed in a subject, the first of these scans will be used to select pre- and post-scan NIHSS scores.

Logistic regression with correlated measures

This model will be used to estimate the odds ratio describing the global favorable outcome, and to estimate the odds ratio of achieving mRS 0-1 at Day 90 in the context of repeated measures.

Statistical Analysis Plan: Alteplase—Genentech USMA
46/ML29093 5/17/2017

The model is specified as follows:

- Let Y_{ik} , be the correlated binary outcomes (1 = favorable outcome, 0 = unfavorable outcome) for patient i , and let $E(Y_{ik}) = \mu_{ik}$ be the marginal means of the outcomes conditional on the patient-specific covariates, including treatment.

For the analysis of the global favorable outcome, $k=1, \dots, 4$ will index the 4 dimensions (mRS, NIHSS, BI, and GOS).

For the analysis of mRS 0-1 $k=1, 2$ will index the repeated evaluations of mRS (Day 30 and Day 90).

- The linear predictor will include an outcome-specific intercept α_k , treatment T_i , and the explanatory variables X_i . The link function transforming the marginal mean outcome μ_{ik} into the linear predictor will be the logit function:

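### The adverse event summaries have three end points that do not agree, and the missing-month rule can date an on-study event about 11 months late

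*SAP*

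**What the plan says.** **Cut-offs.** Section 4.6 removes adverse events "with onset after Day 90 assessment, will be listed as non-treatment emergent and will not be included in the safety summaries", so an event on the day of the assessment stays in. Section 4.6.2 has two further rules in one paragraph: "AEs occurring after receipt of any study medication and before Day 90 will be summarized", and then "SAEs, ICH, AEs of special interest and AEs leading to study treatment discontinuation will be summarized through Day 90". Section 2.2.4 lists the exploratory safety measure "Stroke recurrence (based on AE monitoring) within 90 days". On the visit itself, Section 4.4 notes: "The protocol allows this visit to be scheduled within 14 days of the target 90 days post-treatment". The Appendix B schedule gives the same window, which is Day 76 to Day 104.

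**Partial dates.** Section 4.6.2 ties the period to imputed dates: "Timing of the AEs relative to Day 30 and Day 90 will be determined, using imputation for partial AE start and stop dates if necessary". Appendix D then states: "A missing month/year in a start date will be imputed by the month/year of randomization". A missing start day becomes the first of the month, with randomization as the lower limit. No upper limit is given, and no check against a year that was recorded. For stop dates: "A missing month in a stop date will be imputed by the month of the last contact".

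**The concern.** Two programmers who follow this SAP could build different serious-event and recurrence tables from the same data, because the sections do not end the period at the same point. Stroke recurrence is identified only through adverse event reporting (Sections 2.2.4 and 4.6.2.2), so the filter bears directly on a named outcome.

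The partial-date rule is a separate fault. Imputing a start month is normally meant to be cautious and to keep a doubtful event inside the treatment-emergent period. Here, when follow-up crosses a year end, the rule can do the opposite and push an event that must have started on study well past its end.

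**Working it through.** The SAP gives no figure on this point to reproduce. The check sets the rules side by side and works through the calendar. Study days below count randomization as day 0.

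**1. Cut-offs, if Day 90 in Section 4.6.2 is a study day**

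| Visit on | Onset on | 4.6 | 4.6.2, all events | 4.6.2, serious events, hemorrhage, special interest |
|---|---|---|---|---|
| Day 76 | Days 77-89 | out | in | in |
| Day 76 | Day 90 | out | out | in |
| Day 104 | Day 90 | in | out | in |
| Day 104 | Days 91-104 | in | out | out |

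**2. Cut-offs, if Day 90 in Section 4.6.2 is the visit**

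Sections 4.6 and 4.6.2 then differ only for an onset on the visit day: kept by 4.6, dropped by the rule for all events, kept by the rule for serious events. But the period runs 76 to 104 days by patient, up to 14 days either side of 90 (14/90 = 15.6%), while recurrence is defined over 90 days.

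**3. Missing start month, read item by item**

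Inputs: the month is missing and takes the randomization month; the recorded year is kept; the day is missing and becomes the 1st, not before randomization. All randomization dates in 2014 and 2015 were enumerated, with every onset from day 0 to day 90.

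- *Same calendar year as randomization:* no event is pushed out of the period.
- *Following calendar year:* every event is pushed out. The imputed day is 335-365 for 2014 randomizations and 336-366 for 2015, where the next year is a leap year.
- *Largest delay:* true onset 1 January, imputed 1 December = 334 days, or 335 in a leap year. *Smallest delay:* true onset 31 March after randomization on 31 December, imputed 1 December = 335 - 90 = 245 days in a common year.
- *Randomization dates exposed:* 3 October to 31 December, 90/365 = 24.7%.
- *Pairs of randomization day and onset day that cross the year end:* (1 + 2 + ... + 90)/(365 × 91) = 4,095/33,215 = 12.3%.

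The last two shares describe the calendar. They are not rates of affected events, because the month must also be missing.

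Example: randomized 20 December 2015, true onset 5 January 2016 (day 16), start recorded only as 2016. The rule gives 1 December 2016, which is day 347 and 331 days late. The event is past every cut-off in Sections 4.6 and 4.6.2.

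**4. Missing start month, with month and year replaced as a pair**

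The same event becomes 1 December 2015, raised to 20 December 2015 by the randomization limit. It stays in the summaries, but the recorded year is overwritten. A true Day 60 non-serious event handled this way would also enter the 30-day summary in Section 4.6.2. The SAP does not say which reading applies.

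**5. With the bounded rule**

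The earliest date consistent with the year 2016 and not before first study drug is 1 January 2016 (day 12). Such a date is never later than the true onset, so no on-study event is moved past the cut-off.

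**The case against.** **Day 90 is often a visit label in this SAP.** Section 4.2 equates completing Day 90 with completing the study, and Appendix D speaks of Day 90 assessments. On that reading Sections 4.6 and 4.6.2 nearly agree. This stands as a limit on the first part. It leaves the visit-day difference and the mismatch with outcomes defined over 90 days. Section 4.6 also names the assessment explicitly where Section 4.6.2 does not.

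**Events after an early completion visit may not be collected.** The SAP refers the reporting period to the protocol, which is not at hand. The Day 76 case therefore matters only if later events are reported. The Day 104 case does not depend on this.

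**The date fault needs a coincidence:** month missing, year recorded, and onset in the next calendar year. That is right, and the SAP gives no frequency. Rapid reporting of events of special interest (Section 4.6.2.2) makes an unknown month less likely for recurrence.

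**Stronger readings that the document does not support.**
- A reader might infer that real events will be lost. That is possible under one reading of Appendix D, but not shown.
- A reader might infer that mortality or the primary safety outcome is distorted. Deaths have their own summaries (Sections 4.6.2 and 4.6.6), and 36-hour symptomatic hemorrhage has its own timing rules in Appendix D.
- A reader might infer that patients without a Day 90 assessment lose events. Under Section 4.6 nothing can fall after an assessment that did not happen, so nothing is removed.
- A reader might infer that the stop-date rule removes events. It can give an impossible date (stop year 2015, last contact March 2016, imputed March 2015), but the filter works on onset.
- Ending the general adverse event tables at the completion visit is a defensible choice in itself. The fault is that the SAP does not make one choice.

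**Conclusion.** The point holds in two limited parts.

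First, the adverse event cut-offs do not agree. If Day 90 is a study day, events up to 14 days either side of it are classified differently by Sections 4.6 and 4.6.2. If it is the visit, the disagreement shrinks to the visit day, but the period does not match the 90-day definition of stroke recurrence.

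Second, the missing-month rule is unsafe across a year end. Read item by item, it dates a year-crossing event 245 to 335 days late, at study day 335-366, and always outside a 90-day period. Read as a pair, it contradicts the recorded year. This rests on the day and month being missing with the year known, and on onset within 90 days of randomization.

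The number of events affected cannot be derived from the SAP and is probably small. Events that are excluded remain in listings. This is a correction worth making before database lock, not a threat to the main safety conclusions.

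**What to change.** - **Sections 4.6 and 4.6.2:** state one end point for the adverse event summaries, say whether it is study day 90 or the visit, and use the same inclusivity for all event types. Derive adverse event outcomes defined over 90 days, such as stroke recurrence, on study day 90 whatever the visit date.
- **Appendix D, start dates:** impute the earliest date consistent with every recorded part and not before first study drug.
- **Appendix D, stop dates:** impute the latest date consistent with every recorded part and not after last contact.

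The start-date rule also covers a missing year. At present, an onset of 5 January with no year, after randomization on 20 December 2015, is dated 5 January 2015, which is 349 days before randomization, because the lower limit is written only for a missing day.

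The cost is a few sentences and a small derivation change. The downside is that some events after Day 90 may move from a summary to a listing.
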